Modifications: Any change in this research project or materials must be submitted on a Modification application to the IRB for prior review and approval, except when a change is necessary to eliminate apparent immediate hazards to subjects. The investigator is required to promptly notify the IRB of any changes made without IRB approval to eliminate apparent immediate hazards to subjects using the Modification/Update Form. Modifications requiring the prior review and approval of the IRB include but are not limited to: changing the protocol or study procedures, changing investigators or funding sources, changing the Informed Consent Document, increasing the anticipated total number of subjects from what was originally approved, or adding any new materials (e.g., letters to subjects, ads, questionnaires).

Unanticipated Problems Involving Risks: You must promptly report to the IRB any unexpected adverse experience, as defined in the IRB/HRPO policies and procedures, and any other unanticipated problems involving risks to subjects or others. The Reportable Events Form (REF) should be used for reporting to the IRB.

Audits/Record-Keeping: Your research records may be audited at any time during or after the implementation of your project. There are Federal, State and Institutional requirements for record retention. Check with your organization and your funding agreement to learn more about what record retention requirements apply to your project.

Additional Information: Complete information regarding research involving human subjects is available in the "Washington University Institutional Review Board Policies and Procedures." Research investigators are expected to comply with these policies and procedures and to be familiar with the Belmont Report, 45CFR46, and other applicable regulations prior to conducting the research. This document and other important information is available on the HRPO website http://hrpo.wustl.edu/.

Aim 3: BREASTChoice RCT

PI: [name] IRB ID #: 202005217

Project Details

1. Demographics

1.1 Project Title:

Implementing Breast Reconstruction Clinical Decision Support in Diverse Practice Settings

1.2 Short Title (required):

Aim 3: BREASTChoice RCT

1.3 Project is primarily:

Social Science/Behavioral (includes History/Anthropology)

1.4 Type of Study:

Other Interventional

1.4.a Is your research study one in which one or more human subjects are prospectively assigned to one or more interventions (which may include placebo or other control) to evaluate the effects of those interventions on health-related biomedical or behavioral outcomes (NIH clinical trial definition).
Yes

- **1.5** Select how you plan to obtain consent:
 - Sign a consent document or a consent letter
 - Letter or information sheet with no signature
 - Script for use either in person or over the phone with no signature

2. Source(s) of Support

2.1 Source(s) of Support

Type/Source	Grant Title	Name of PI on Grant	Status
Federal Agency	Implementing Breast Reconstruction Clinical	[name];	AWARDED
Agency for Healthcare Research	Decision Support in Diverse Practice Settings	[name]	
& Quality (DHHS)			

3. Research Team

 - Public Health
 - Surgery
 - Plastic
- **1.3** Provide a short summary/abstract of the purpose and procedures of the study proposed in this IRB application.
 - DO NOT include information on studies not proposed in this application.
 - Use LAY terminology only. This must be easily understandable by IRB community members and nonscientists.

 DO NOT cut and paste technical abstracts from source of support applications that may not be understood by a general audience.

Purpose:

Breast reconstruction after mastectomy is a highly personal decision. Although it can restore quality of life for many, there are numerous risks associated with the procedure. The risk of complications exceeds that of most elective procedures. A clinical decision support tool, BREASTChoice, with personalized risk information and patient preferences, was created to be used to address these issues. The randomized control trial will evaluate whether the implementation of BREASTChoice into usual care is more effective than a control website, at improving the quality of reconstruction decisions.

Procedures:

This study aim will evaluate the effects of BREASTChoice on post-mastectomy breast reconstruction decision quality, decisional conflict, and treatment choice in a multi-site randomized trial. After receiving their breast cancer diagnosis from their breast surgeon and (when possible) before their plastic/reconstructive surgery visit discussing breast reconstruction, participants will receive a link to the BREASTChoice tool or control website through MyChart or email if they do not have a MyChart account. Depending on the clinic work-flow, the patients may be sent the tool or control website: 1) by email, prior to their visit with the plastic or reconstruction surgeon, for them to complete from home or in the waiting room (ideal and preferred approach); 2) by email or link, in person or virtually at the time of their plastic or reconstruction visit, for patients that have same-day breast surgeon and plastic reconstruction surgeon visits, with time to wait in between appointments; or 3) by email, after the plastic surgery appointment, if they have not yet made a decision about reconstruction after mastectomy (e.g., if they are undergoing neoadjuvant chemotherapy, or they want or need more time to decide on their surgery choices).

Participants in the intervention group will complete BREASTChoice, and a summary of their risks and preferences will be sent to their plastic/reconstructive surgeon to view in the electronic health record. All participants will be sent a link to complete an online survey after their plastic/reconstructive surgery visit. After enrollment, we will monitor participants' breast reconstruction receipt including whether they opted to have breast reconstruction, and if so, the type and timing of reconstruction.

Clinicians will be trained on BREASTChoice tool functions and how the tool is integrated into EHR. We will assess clinicians' shared decision making pre - and post-trial.

Prior to the beginning of the Randomized Control Trial (RCT), a pilot phase will be launched. The purpose of the pilot phase is to test the workflow and procedures. We plan to recruit up to 20 patients, continuing until procedures are smooth and ready for the randomized trial. We will follow the same procedures as the trial (above), other than randomization, to test the workflow and tool use programming.

1.4 Specify your research question(s), study aims or hypotheses:

The main hypotheses of this study is that a workflow - aware clinical decision support tool, BREASTChoice, is more effective than a control website at improving the quality of breast reconstruction decisions among women with stages 0-III breast cancer, eligible for post-mastectomy breast reconstruction.

The goal of this aim is to evaluate the effects of the updated BREASTChoice on decision quality, decisional conflict, and treatment choice in a randomized controlled trial in a diverse population. Patients considering mastectomy will be randomized to BREASTChoice or an informational website.

1.5 Background and significance and/or Preliminary studies related to this project:

Decisions about whether to have breast reconstruction following a mastectomy due to breast cancer, when to have it, and what type of reconstruction are often discordant with patients' personal preferences about risk, appearance, recovery, and number of surgeries. There are currently no reliable methods for integrating patient-specific information into the clinician-patient encounter to personalize these decisions. Incomplete or insufficient information could lead to unexpected complications, additional operations, and decision regret. Compared to most elective procedures, major complications from breast reconstructive surgery are high. As many as 50% of patients having reconstruction, experience wound complication and about 15% of patients experience complications that require additional surgeries. For some patients, complications lead to 15-20 additional procedures.

Patients often lack knowledge of complication risks for reconstructive surgery. This lack of knowledge can lead to poor satisfaction and regret. In one study, only 15% of patients understood potential risks and complications of post-mastectomy reconstruction options. Additionally, gaps exists in how breast reconstruction decision – making is addressed between clinicians and different populations. For example, Black women report unmet information needs and have greater knowledge deficits about reconstruction. Older (65+) women are less likely to be offered reconstruction compared to younger women.

Due to the higher risk of major complications from reconstructive surgery, and gaps in the decision making process, the BREASTChoice (Breast Reconstruction Education And Support Tool) tool was developed in our earlier work. The BREASTChoice tool helps women, who are undergoing a mastectomy, make decisions with their clinician about reconstructive surgery based on their personal risk factors and preferences.

BREASTChoice incorporates personalized, predictive risk analytic modelling, developed and validated using institutional and national claims data from over 17,000 patients. The tool is an interactive website and can be sent through My Chart and integrated into the electronic health record. The formative work on this tool and subsequent pilot testing demonstrated an increase in self-reported knowledge for patients in the intervention group, and usability was high.

1.7 Describe EACH of your participant populations

- Include description of any control group(s)
- Specify the Inclusion/Exclusion criteria for EACH group

Adult women (18+) in one of the study sites over an 18-month period, with a diagnosis of incident or recurrent stage 0-III breast carcinoma will be eligible.

We will exclude patients with Stage IV disease (treatment is primarily medical, not surgical) or histology type besides ductal/lobular carcinoma (e.g.,phyllodes, sarcoma; these rare tumors differ in treatment and prognosis). We will exclude patients who have had prior mastectomy and are seeking delayed reconstruction, so that we can evaluate decisions about reconstruction timing. We will exclude those without a malignancy (i.e., considering mastectomy for prophylaxis only) because their reconstructive surgery visit or surgery may occur long after the initial consultation. We will exclude patients who cannot give informed consent or use our study materials due to self-reported or observed cognitive, visual,

or emotional barriers.

Plastic and reconstructive surgeons working at Barnes Jewish Hospital Siteman Cancer Center, Barnes Jewish West County, and Christian Hospital North East, who provide breast reconstruction after mastectomy, are eligible for this study.

We will exclude plastic and reconstructive surgeons working at other breast clinic locations, and surgeons who do provider breast reconstruction care to patients who have undergone a mastectomy due to breast cancer.

- **1.8** Check all materials/methods that will be used in recruiting participants:
 - Telephone script
 - Ads/Brochures/Posters/News Release/Fliers
 - · Email or letters
 - Website or Social Media (printed pages)
 - Other Materials Video describing study to put on study website
 - · Medical Records or Other PHI
 - Epic MyChart

Attachment Name	Category	Version	Date Attached
R18 surgeon screening email 9.3.2020clean.rtf	Recruitment: Email or letters	3	09/03/20
R18 Patient Phone Script screening 6.8.21.rtf	Recruitment Script: Phone	10	06/11/21
MyChart email message to patients Aim 3 4.28.21.rtf	Recruitment: Email or letters	11	04/29/21
R18 Aim3 Flyer 3.22.21 (3).rtf	Recruitment Materials: Ads/Brochures/Posters/News Release/Fliers	11	09/12/21
Website 7.27.21.rtf	Recruitment: Website	1	07/27/21
BREASTChoice Recruitment Video (HD 1080 - WEB (H264 4000)).mp4	Recruitment: Other	2	09/17/21

1.8.b List the individual data elements you will access from the medical records (or other source of PHI) to identify potential participants for recruitment and, if applicable, any individual data elements that you will include on a screening log prior to consent.

We will review medical records for names, age, race, telephone numbers, mailing addresses, email addresses, language spoken at home, and breast cancer diagnosis stage and previous breast cancer surgery.

We will collect participants' reconstruction decision from the electronic health record after enrollment.

1.8.c What is the plan for individual identifiers obtained to identify participants and, if applicable, those identifiers maintained on a screening log prior to consent?

Identifiers for those who do NOT enroll will be destroyed at the earliest opportunity, consistent with the conduct of the research (for example when recruitment and enrollment are completed.)

- 1.8.d Does the research team agree that the requested information will not be reused or disclosed to any other person or entity, except as required by law, for authorized oversight of the study, or for other research for which the use or disclosure of the requested information would be permitted by the HIPAA Privacy Rule?
 Yes
- **1.10** Describe where the consent discussion will occur (check all that apply):
 - By phone
 - Online
- **1.11** Participants and/or their legally authorized representative will have (check all that apply to the consent process and explain process in Question 1.12 below):
 - Limited time based on when they must be treated clinically or when research procedures begin. However they:
 - Will have an opportunity to thoroughly review the consent materials with knowledgeable members of the research team, with family and/or friends as appropriate
 - Will have sufficient time to have all of their questions answered
 - Will not be asked to consent when under the influence of drugs that have the potential to impact cognitive abilities such as sedation.
 - Will not be asked to consent at a time when they may be unable emotionally to fully consider the consent information (e.g. immediately following significant diagnosis.)
- **1.12** Provide a description of the enrollment and consent process in sequential order and address EACH of the bulleted points below:
 - Describe each study population separately including control population
 - Describe when recruitment and consent materials are used
 - Indicate how much time individuals will have to consider participation
 - If eConsent will be used to obtain an electronic signature, describe how the eConsent will be presented to participants, how their questions will be answered and how the participant will receive a copy of the final, signed consent

• Describe the steps that will be taken by the research team to minimize the possibility of coercion or undue influence during the consent process

The WU project coordinator will screen through EPIC to identify potentially eligible patients at the participating study sites. They will retrieve the phone numbers, email addresses if available, and mailing addresses of potentially eligible patients. Patients will be contacted after the patient has received their breast cancer diagnosis.

Then WU research staff can approach eligible patients by phone, after the breast surgery visit and before the reconstructive surgery visit to provide study information. The patient can choose to complete the consent form 1) in clinic (with signed consent document), 2) virtually (waiver of documentation of written consent by providing an information sheet electronically), or the 3) WU research staff can review the consent information sheet with them over the phone or zoom. The waiver of documentation of consent will be sent via secure email or MyChart (process approved by the MyChart, Epic1, and BJC clinical informatics teams).

Because of the public health response to COVID19, we anticipate that some patients will have virtual clinical encounters instead of in-person clinical encounters. If this occurs during the trial, participants would be offered electronic waiver of documentation of informed consent information sheets or phone consent instead of paper consent forms. Study staff will be available through phone, zoom or email to answer the participants' questions.

Depending on the circumstances (as described in the following), WU research staff may approach potential participants in one of three ways.

- 1) If potential participants may be reached prior to their visit with the plastic or reconstruction surgeon, they will be approached virtually, by phone, or in-person at the clinic before their appointment (preferred method).
- 2) For some participating sites that have same-day breast surgeon and plastic surgeon reconstruction visit clinic work-flows, the study staff will not have a chance to contact these patients by phone for consent prior to their visit with their plastic/reconstructive surgeon. These potential participants will be approached in person or virtually by the study staff to provide information about the study and complete informed consent. Potential participants contacted virtually will be sent e-consent forms.
- 3) Some potential participants may be approached after their breast reconstruction visit (but before they make their reconstruction decision) due to clinic workflows that have same day breast and reconstruction surgeon visits, or clinics that add a patient visit to the clinic schedule that day. These patients with same day breast surgeon and breast reconstruction appointments will complete consent and study procedures after the reconstruction visits and before their next reconstruction visit or surgery.

For recruitment, we will approach WUSM faculty who see patients that are eligible for the study. Before the study began, [name] and [name] presented the information about the study to WUSM's Department of Surgery's Division of Plastic and Reconstructive Surgery. At the meeting, clinicians expressed interest in participating in the study. We will retrieve eligible clinician email addresses and/or phone numbers from the WUSM system.

Eligible surgeons will be emailed by WU research staff with study information. If interested the research coordinator will call the surgeon and review the phone consent information sheet. The surgeon could alternatively request a waiver of documentation of informed consent or complete the consent in-person.

1.13 Provide a detailed description in sequential order of the study procedures following the consent process - DO NOT cut and paste from the Consent Document.

Describe study populations separately if they will be participating in different procedures

DESCRIBE:

- · Control populations, if applicable
- Any randomization, if applicable
- What participants will be asked to do/what happens in the study (in sequential order)
- The time period over which procedures will occur
- · Long-term follow-up and how it occurs

After the patient participant consents to be in the study, we will randomize (using computer random assignment, RCT only) participants to view the clinical decision support tool, BREASTChoice or the attention control website (https://www.cancer.gov/types/breast/reconstruction-fact-sheet), using block randomization (block size 4). Depending on the clinic work-flow, the patients may be sent the link to the tool or control website: 1) by email or MyChart message, prior to their visit with the plastic or reconstruction surgeon, for them to complete from home or in the waiting room (ideal and preferred approach); 2) by email or MyChart, in person or virtually at the time of their plastic or reconstruction visit, for patients that have same-day breast surgeon and plastic reconstruction surgeon visits, with time to wait in between appointments; or 3) by email or MyChart, after the plastic surgery appointment, if they have not yet made a decision about reconstruction after mastectomy (e.g., if they are undergoing neoadjuvant chemotherapy, or they want or need more time to decide on their surgery choices). Participants will be sent the link via MyChart unless they do not have a MyChart account. In that case, they will be sent the link via email. Study staff will be available to answer questions about MyChart via phone or email.

The following privacy protections will be enacted for all email communications involving PHI; 1) a test email will be sent to the participant to verify their identify (confirm correct recipient) and that this email will be sent in a secure manner (i.e., [secure] in subject line); 2) The body of the email will instruct the participant to send all information as a response to this thread and to not remove the "[secure]" from the subject line; 3) document in your research records the participant's agreement to provide information over email.

We will randomly choose to audio-record the visits of 20% of participants with their plastic surgeon. We have included in our consent documents for patients and clinicians that their visit may be audio recorded. As part of the consent documents we ask participants if they are willing to have their visit audio recorded. If they say no, they can still be a part of the study.

Clinicians who consent to participate in the trial will receive a brief virtual training on how BREASTChoice functions and the features, including placement of the patient tool summary in the electronic health record. Clinicians will complete pre/post trial survey about shared decision making. Clinician survey participation will take less than 5 minutes. They will receive a \$50 gift card as a thank you for their time.

BREASTChoice will be hosted in a secure location with a secure database, integrated with Epic by the BJC Center for Clinical Excellence decision support informatics team. This team is working closely with the Epic team for security compliance. The tool will use security authentication procedures, data encryption, the app Orchard, and exchange information using Fast Healthcare Interoperability Resource (FHIR). The tool will undergo and receive approval through the hospital security review process, which includes a vulnerability scan.

The tool will auto-populate patient health information from the electronic record. Participants can modify their personal health information in the tool in case data such as current health conditions listed in their record are out-of-date, but cannot modify their personal health information in the electronic medical record. Participants can view a summary at the end of BREASTChoice that includes the tailored risk information and their values and preferences. The summary will be sent to their clinician to view in the electronic health record, via the Epic portal. After patients view the BREASTChoice tool or attention control website, all participants will complete an online survey assessing socio-demographics, knowledge, values/preferences, health literacy, decisional conflict, measure of patient engagement, health-related quality of life, preferred decision role, consult time and usability of the tool. All measures were chosen based on their short length so as not to burden participants. After enrollment, we will monitor reconstruction receipt including type and timing, and assess clinician satisfaction after Aim 3 study recruitment is complete.

Participation is expected to take about 25 minutes. Participants will receive a \$20.00 gift card as a thank you for their time.

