The primary endpoints of knowledge, preference concordance, and decisional conflict will first be evaluated with univariate analyses through the use of t-tests and chi-square analyses as appropriate. We will explore the use of transformations and non-parametric alternatives for these responses if necessary. We will use generalized linear mixed models to explore differences between patients randomized to BREASTChoice and to the control arm. Models will be adjusted for important clinical and demographic variables and will include relevant interactions. Specifically, we will include an interaction between group (i.e., BREASTChoice or control)and time, to test for differences in randomized group over time that could be due to changes in surgeon practices. A random effect for surgeon will also be included in the model. Missing data will be handled through imputation, and associations between covariates and the missing indicator will be explored. The same analytic procedure will be used to examine the impact of BREASTChoice on patient engagement (CollaboRATE).

A secondary goal is to explore whether the intervention is associated with fewer high-risk patients choosing reconstruction. Patients will be considered high-risk if their risk exceeds 2 times the population average.38 We will explore whether age or race modifies the association between intervention and decision quality (knowledge and preference concordance). Descriptive statistics will be calculated for these outcomes, and associations will be assessed using appropriate chi-square or Fisher's exact tests.

We also will explore whether provider intention to engage in shared decision making increases during the trial, by examining changes in the mean of the CPD-Reaction scale, through the use of the Wilcoxon signed-rank test. Preferred decision role will also be assessed through chi-square or Fisher's exact tests.

Provide the rationale or power analysis to support the number of participants proposed to complete this study. The sample size needed to detect an effect size of 0.3 and power of at least 80% in decisional conflict, comparable to what was seen in a similar study,122 is 170 per group. With this sample size,the study will be adequately powered to detect at least a 15% difference in the percent of patients with knowledge scores > 50%, assuming that the control group percentage of patients scoring > 50% is 34%.

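### Visit status at consent is neither a randomization stratum nor a named model term, and the plan does not say whether a randomized patient who decides before a delayed link goes out is still sent it

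*Combined protocol and SAP*

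**What the plan says.** Item 1.12 describes three ways of approaching patients: before the reconstruction visit (preferred), on the day of a combined visit, or after the reconstruction visit but before the patient has decided. The last group "will complete consent and study procedures after the reconstruction visits and before their next reconstruction visit or surgery".

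Item 1.13 gives the order of events. "After the patient participant consents to be in the study, we will randomize", by computer in blocks of 4, with no stratification factor named. The link to BREASTChoice or the control website is then sent before, at or after the visit, depending on clinic work-flow. The third route is worded as conditional: "by email or MyChart, after the plastic surgery appointment, if they have not yet made a decision about reconstruction after mastectomy".

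Item 1.22 sets out the analysis of the three primary endpoints (knowledge, preference concordance, decisional conflict). "Models will be adjusted for important clinical and demographic variables and will include relevant interactions". The only terms named beyond that are a group-by-time interaction and a random surgeon effect. Missing data are to be imputed.

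The power rationale after item 1.22 reads: "The sample size needed to detect an effect size of 0.3 and power of at least 80% in decisional conflict", for which the number given "is 170 per group".

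On the survey, item 1.3 sends it to all participants after the plastic surgery visit, and item 1.13 places it after patients have viewed their website.

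**The concern.** There are two separate issues.

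**Precision.** Patients who enter after the visit are, by the plan's own entry rule, those who have seen the surgeon and are still undecided. Patients who enter before the visit have not been filtered in this way. A group selected for indecision is likely to differ in decisional conflict whichever arm it is in. Visit status is known at consent, so it can be used in both the randomization and the model at almost no cost. Leaving it out gives away some precision in a trial with little power to spare.

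**Delivery after allocation.** For a patient randomized before the visit, the condition on the post-visit route could come into play after allocation if her link is delayed. The plan does not say whether she is still sent the link if she decides at the visit. The two links are visibly different and no blinding of the staff who send them is described, so any discretion would be used with knowledge of the arm. If decided patients were not sent BREASTChoice, the average effect would be diluted. The gap matters more because item 1.13 places the survey after viewing the website, and no section states that all randomized patients are analysed as randomized.

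**Working it through.** **Inputs from the power rationale:** effect size 0.3 SD, power at least 80%, 170 per group. **Assumed:** two-sided 5% test, since no alpha or sidedness is given. **Not in the documents, so shown as ranges:** the share s of patients entering after the visit (20-40%), the difference k in decisional conflict between visit-status groups (0.3-0.8 SD), and the share of the BREASTChoice arm not sent the link (5-10%).

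**1. The plan's own figure.** Normal approximation: n = 2 × ((1.960 + 0.842)/0.3)² ≈ 174.4, so 175 per group. With 170 per group, power is 79.0% by the normal approximation and 78.8% by the noncentral t. The stated 170 is reproduced to within 3%, with power marginally below the stated level. The noncentral t is used below.

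**2. Gain from adjusting for visit status.** With total SD = 1, a two-level factor explains R² = s(1 − s)k² of the variance. The adjusted effect is d = 0.3/√(1 − R²).

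| s | k | R² | adjusted d | power |
|---|---|---|---|---|
| no adjustment | – | 0 | 0.300 | 78.8% |
| 0.2 | 0.3 | 0.0144 | 0.302 | 79.3% |
| 0.3 | 0.5 | 0.0525 | 0.308 | 80.9% |
| 0.4 | 0.8 | 0.1536 | 0.326 | 85.0% |

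The gain is 0.5 points at the low end, 2.1 in the middle case and 6.2 at the top. The top needs both the largest share and the largest difference. If visit status explains 1-10% of the variance, the gain is about 0.4-4 points (79.2% to 82.8%).

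**3. Dilution if decided patients were not sent the link.** If a fraction q of the BREASTChoice arm gets no link and no benefit, the average effect is 0.3(1 − q).

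- q = 5%: 0.3 × 0.95 = 0.285, power 74.5%
- q = 10%: 0.3 × 0.90 = 0.270, power 69.9%

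Stratifying or adjusting does not recover this loss, because the effect itself is smaller. It needs its own remedy, a rule on sending the link.

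**The case against.** **Everyone is surveyed after the visit.** Under item 1.3, every patient has been counselled by the time the endpoints are measured, so counselling alone does not make post-visit entrants different. This stands. The case for visit status rests instead on their having been selected as undecided. The size of that difference is unknown.

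**The model may already capture part of it.** The random surgeon effect and the unnamed covariates could absorb some work-flow differences. This also stands, and it is one reason to expect a modest gain.

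**A reader might infer that the primary endpoints are open to selection bias after allocation.** The documents do not establish this. For patients approached after the visit, item 1.12 applies the undecided condition at approach, before consent and so before randomization. Route is tied to clinic work-flow, and no section says that staff choose it after seeing the allocation. That a decided patient would be sent nothing is an inference from silence; no section drops her, and item 1.3 sends the survey to everyone. The exposed case (randomized before the visit, link delayed, decision made meanwhile) is narrow and its frequency unknown. A null simulation that dropped decided patients (30% on the late route, correlation 0.5 between outcome and decision) gave a bias of about zero when 30% had decided in both arms and about 0.01 SD with 30% versus 50%. Nor can the assumed 0.3-0.8 SD be turned into a bias by supposing that routes differ between arms. It is a prognostic difference, which randomization balances, and not an effect of late delivery.

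**A reader might also see a contradiction in item 1.12** between approaching patients before they decide and finishing procedures before the next visit or surgery. The first limits approach and the second limits completion, so they do not conflict.

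**Conclusion.** The point holds as a modest design improvement plus one missing rule. Visit status at consent is known before allocation, is plausibly related to decisional conflict, and is used in neither the randomization nor the named model terms. Using it would raise power from 78.8% to 79.3-85.0% under the assumed shares and differences. About 0.5-4 points is realistic, and the surgeon effect may already capture part of it.

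The silence about a patient who decides before a delayed link goes out could cost more (power about 75-70% if 5-10% of the BREASTChoice arm were not sent it), but only if such patients were in fact left out, which the documents do not say. All of these sizes rest on a two-sided 5% test and on inputs that the documents do not supply. Confidence is medium.

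**What to change.** 1. Before the allocation is generated, record whether the reconstruction visit has taken place and confirm that the reconstruction decision is still open.
2. Run the permuted blocks within two strata: visit still to come, and visit already held.
3. Include visit status at randomization as a fixed effect in the models for knowledge, preference concordance and decisional conflict. Do not use the delivery route actually taken, because that can be settled after allocation.
4. State that every randomized patient in both arms is sent the link and the survey with no further check on decision status, and is analysed as randomized.

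The completion limit in item 1.12 can stay as it is.

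The cost is two fields on the randomization form, one more block list and one model term. The downside is that a few links will go to patients who have already decided. For them the website may no longer affect the choice, so step 4 closes the discretion and keeps the comparison intact but need not recover all of the diluted effect.
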